4.0 Study Endpoints*

- The primary study endpoint will be the rewarming of frostbitten extremities for 30 minutes at 38°C.
- The secondary study endpoint will be a survey regarding ease of use of this rewarming modality.
- The primary safety endpoint will be patient pain or discomfort that is determined to be unrelated to the discomfort known to be associated with rewarming frostbitten tissue. Two consecutive temperature measurements above 42°C will prompt the cessation of the SVR.

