6.0 Procedures Involved*

- Patients presenting to the ED at Dartmouth-Hitchcock and external study sites with acute frostbite (tissue still frozen) of the hands and/or feet will be identified and approached for recruitment. Patients not entering the study will continue to be treated by ED providers in the traditional fashion.
- Patients recruited for the SVR study will be consented to have their circulating warm water bath(s) heated by the novel SVR method. Providers or nurses caring for the study subjects will be consented to participate and will 1) conduct the SVR procedure, and 2) complete a questionnaire. A researcher will gather SVR equipment and attach two thermometers on the basin: one on the side nearest the SVD, the other on the opposite side. The researcher will verbally walk the provider or nurse carrying out the SVR through the following steps. A 15 L Sterilite® basin will be filled to the marked line (12cm) with water from jugs at room temperature, for each frozen extremity. One extremity can be rewarmed in a single basin, with the possibility for up to four simultaneous SVR basins for a patient with frostbite of all hands and feet. The SVD will be attached to the distal edge of the basin, with one SVD per rewarming basin. The SVD will be turned on and set to maintain the bath at a constant 38°C for 30 minutes duration. The thermometers will be powered on continuously and the researcher will record temperatures simultaneously from each thermometer and the SVD every 2 minutes. At the end of the 30 minute treatment, the extremity will be assessed by the researcher for warmth and pliability. If the extremity still feels cold or frozen, an additional 30 minutes in the water bath will commence, with

PROTOCOL TITLE: Assessment of Sous Vide Water Baths for Acute Rewarming of Frostbitten Extremities.

subsequent reassessment. Rewarming will be considered complete when the affected tissue becomes red or purple, soft, and pliable.

- Patients who do not consent to SVR and elect for traditional water bath management will be asked for their consent to record the similar demographic, water temperature, and time-to rewarm data as in the SVR treatment arm. After re-warming is complete, the provider will be asked to fill out a survey regarding the ease of use and efficacy of the SVR.
- *Describe:*
 - *Procedures performed to lessen the probability or magnitude of risks.*

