14.0 Withdrawal of Subjects*

- Subjects will be withdrawn without their consent for safety reasons or medical necessity. Criteria as follows: If water bath temperatures are recorded at over 42°C on two consecutive readings during the

PROTOCOL TITLE: Assessment of Sous Vide Water Baths for Acute Rewarming of Frostbitten Extremities.

same treatment phase, if subject is judged by the treating clinician to have pain greater than expected for frostbite rewarming, or if a separate medical issue arises in the subject in which urgent treatment necessitates termination of the research.

- *Describe any procedures for orderly termination.*
 - The SVD will be powered off and the water bath maintained manually by medical staff.
- *Describe procedures that will be followed when subjects withdraw from the research, including partial withdrawal from procedures with continued data collection.*
 - Withdrawal from the research will preclude any further data collection. Data already collected at the time of the withdrawal will be analyzed with other study data but noted that the study terminated prematurely.

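### Section 14 classes heat and pain stops as withdrawal, which ends data collection; sections 4 and 6 treat the same events only as stopping the device

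*Combined protocol and SAP*

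**What the plan says.** Section 14.0 of the combined protocol and SAP begins with involuntary withdrawal: "Subjects will be withdrawn without their consent for safety reasons or medical necessity". Two of its grounds concern the device run: "If water bath temperatures are recorded at over 42°C on two consecutive readings" within one treatment phase, and "if subject is judged by the treating clinician to have pain greater than expected for frostbite rewarming". The third is an unrelated urgent medical problem. For orderly termination, "The SVD will be powered off and the water bath maintained manually by medical staff".

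The section then answers a template prompt about subjects who withdraw, which expressly mentions partial withdrawal with data collection continuing. The answer is "Withdrawal from the research will preclude any further data collection", followed by "Data already collected at the time of the withdrawal will be analyzed with other study data but noted that the study terminated prematurely".

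Other sections bear on the point:

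- Section 4.0 makes excess pain the safety endpoint ("The primary safety endpoint will be patient pain or discomfort that is determined to be unrelated to the discomfort") and says two consecutive readings above 42°C lead to SVR being stopped.
- Section 6.0 says treatment ends for heat or excess pain and standard rewarming follows. It deals separately with a subject who chooses to leave. It places the limb examination at 30 minutes, repeated after a further 30 if needed, and plans a 6-month chart review for complications.
- Section 17.0 names tissue rewarming as a primary outcome, alongside temperature control, and plans descriptive statistics only.

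**The concern.** Stopping the device and leaving the study are different events. After a hot bath or excess pain, the patient is still in the emergency department, is still being rewarmed and has not revoked consent. If section 14.0 is followed literally, recording ends there. A limb stopped before 30 minutes then has no value for a primary outcome.

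The missing results would not be random. They would come from runs in which the bath overheated or the patient met the safety endpoint. Section 15.0 names hot water burns as a hazard, and these are the patients whose later course matters most. In a series this small, one such patient visibly changes the summary.

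**Working it through.** The plan states no figure to reproduce, so the main check is textual, with a short illustration of size.

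**Step 1: the same triggers in three sections.**

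- Section 4.0: two readings above 42°C stop SVR. Nothing is said about leaving the study.
- Section 6.0: heat or excess pain ends the treatment, and standard rewarming takes over. Again nothing is said about leaving the study.
- Section 14.0: heat or excess pain withdraws the subject, and withdrawal ends data collection.

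Section 14.0 is therefore out of line with the other two.

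**Step 2: what would be lost on the literal reading.**

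- The rewarming result, if the stop comes before the 30-minute examination. A stop in the second 30 minutes leaves only the first examination, at which the limb still felt cold or frozen.
- Time to rewarm under manual care. Sections 6.0 and 14.0 provide the care, but no section says its result is recorded.
- Possibly adverse events after the stop and the 6-month review, since section 14.0 states no exception.
- Possibly data on other limbs. Withdrawal is by subject, and section 6.0 allows up to four basins at once.

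Readings and events recorded before the stop are retained.

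**Step 3: a comparison within the plan.** A patient who refuses the device is asked for consent to "record the similar demographic, water temperature, and time-to rewarm data as in the SVR treatment arm". On the literal reading, someone rewarmed manually after refusing would contribute an outcome, while someone rewarmed manually after a device failure would not.

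**Step 4: illustrative size.** Section 2.0 expects 5 to 20 cases, so take N = 5 and N = 20. Assume one limb per case, k = 1 stop with the limb not yet thawed, and all other limbs rewarmed. The number of stops is an assumption. Intervals are exact (Clopper-Pearson) 95%, shown only for scale because the plan calls for none.

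| Handling | Formula | N = 5 | N = 20 |
|---|---|---|---|
| Left out | (N−k)/(N−k) | 4/4 = 100% (39.8 to 100) | 19/19 = 100% (82.4 to 100) |
| Counted as failure | (N−k)/N | 4/5 = 80% (28.4 to 99.5) | 19/20 = 95% (75.1 to 99.9) |
| Manual rewarming counted as success | N/N | 5/5 = 100% (47.8 to 100) | 20/20 = 100% (83.2 to 100) |

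The choice moves the proportion by 100 − 80 = 20 points at N = 5 and 100 − 95 = 5 points at N = 20.

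The chance of at least one stop is 1 − (1−p)^N. For assumed per-case rates p of 2%, 5% and 10%, it is 9.6%, 22.6% and 41.0% at N = 5, and 33.2%, 64.2% and 87.8% at N = 20.

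**The case against.** The strongest reply is that the no-further-data sentence answers a prompt about subjects who withdraw, while the safety criteria stand in a separate bullet. It may be meant only for people who choose to leave. Sections 4.0 and 6.0 support that intention. This stands as a possible reading. Against it, section 14.0 itself uses the word withdrawn for the safety stops, the data sentence is unqualified, and the prompt's option of continued data collection was not taken up.

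A reader might infer that a stopped limb certainly gets no result and no follow-up. The documents do not settle that. Section 18.0 puts the study on hold pending review after an unanticipated event possibly due to the device, and has data reviewed after each subject. Section 19.0 covers consented chart access for adverse events and outcomes. The 6-month review in section 6.0 applies to enrolled subjects, with no stated exclusion for stopped runs. The data collection forms, which might address this, are not in the text available.

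A reader might also infer that the trial would report an unqualified 100% after a device failure. Section 14.0 says earlier data are analysed and the early stop noted, and the section 4.0 endpoint of 30 minutes at 38°C sits badly with counting manual rewarming as success. Nor is the pain endpoint itself lost, because its occurrence is what triggers the stop.

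Finally, counting every stopped limb as a failure could misclassify one that had already thawed when SVR was stopped for pain. That is correct, and the fix allows for it.

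**Conclusion.** The point holds as a conflict of wording with a selective consequence. Section 14.0, applied literally, would remove the thaw result and could remove the later course for limbs in runs stopped for heat or pain. Sections 4.0 and 6.0 do not require this, and the subject's consent is still in force. The plan does not establish that these data will be lost, only that its text permits it.

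The size depends on a stop rate that the documents do not give. With one assumed stop, the rewarmed proportion differs by 20 points at 5 cases and by 5 points at 20, under the one-limb and all-others-rewarm assumptions. Section 17.0 has no rule on how to count a stopped limb. That is an omission of detail, which becomes consequential only because the series is so small. Severity is minor: stops may well be rare, the analysis is descriptive, and early termination is flagged.

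**What to change.** Leave the heat and pain stops as they are, and change only what follows them.

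1. In section 14.0, call these stops discontinuation of SVR, in line with sections 4.0 and 6.0. Reserve the no-further-data rule for subjects who withdraw consent.
2. After a stop, record whether the limb was thawed at that moment, the time to rewarm under manual care, any burn or other adverse event up to discharge from the emergency department, and the 6-month review.
3. In section 17.0, keep every limb started on SVR in the denominator. Count a limb not thawed when SVR is stopped as not rewarmed by SVR, and report manual rewarming results separately.

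The cost is a few sentences of text, plus one examination and one recorded time per stopped patient. Section 19.0 says that consent already covers chart access for adverse events and outcomes.

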15.0 Risks to Subjects*

- *List the reasonably foreseeable risks, discomforts, hazards, or inconveniences to the subjects related to the subjects' participation in the research. Include as may be useful for the IRB's consideration, a description of the probability, magnitude, duration, and reversibility of the risks. Consider physical, psychological, social, legal, and economic risks.*
 - The standard of care for acute frostbite rewarming, which is a circulating warm water bath, will not be altered and patients will receive the standard of care treatment. The only alteration is the method of maintaining the warm water bath. Frostbite rewarming is known to be a painful process. Pain control will be at the discretion of the treating physician and the study will have no implications on this aspect of care.
 - Potential hazards include hot water burns and the unlikely chance of catastrophic device failure and electrical injury. There were no adverse events reported during the pilot study. Hot water burns are also a risk in the current practice of manual hot water bath management, and the SVD may actually mitigate this risk by improved temperature control. Biomedical engineering at Dartmouth-Hitchcock has assessed the ANOVA SVD.

PROTOCOL TITLE: Assessment of Sous Vide Water Baths for Acute Rewarming of Frostbitten Extremities.

- The investigators do not see any specific psychological, social, or economic risks to the subjects directly related to the research, as the circulating water bath rewarming method is the standard of care for frostbite management.

If applicable, explain how the use of the placebo or non-standard of care therapy may affect risks for participants, addressing the following:

- *The safety and efficacy of other available therapies*
 - The current available therapy for frostbite rewarming is the same as being used in this study – circulating warm water bath. The study will use a new technique to creating this water bath. SVR is expected to be more efficacious than the current method of water bath management.
- *The greatest potential harm that may result from not receiving or delaying effective therapy*
 - While unlikely, it is possible that the SVR would not heat the water and delay time to the current practice of manual water bath management. If this were to occur, delay to therapy would be minimal as the only change in intervention would be the manual addition of warm water to the basin. It is expected that the research treatment will speed up the delivery of effective therapy.
 - Risk will be minimized by assessing the water temperature continuously. The SVR will be ceased and the manual rewarming started if the water bath does not reach the target temperature in 30 minutes, or if the water bath temperature drops below 37°C for more than 5 minutes.
 - If providers are unable to reach an on-call investigator and determine their availability within 20 minutes from the patient expressing interest in the study, standard rewarming will proceed via traditional water exchange practices.
- *If applicable, indicate which procedures may have risks to the subjects that are currently unforeseeable.*
 - Unforeseeable risks different than typical water bath rewarming, if any, would relate to SVD failure. To further minimize this unlikely event the SVD will be physically checked for any signs of wear following each utilization at

PROTOCOL TITLE: Assessment of Sous Vide Water Baths for Acute Rewarming of Frostbitten Extremities.

the time of cleaning. The SVD has been assessed by biomedical engineering at Dartmouth-Hitchcock and deemed low risk.

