1.0 Study Summary

Study Title	Assessment of Sous Vide Water Baths for Acute Rewarming of Frostbitten Extremities
Study Design	Patients with acutely frostbitten hands or feet presenting to the emergency department will be consented to participate in the study. An ANOVA sous vide device will be attached to a water basin and set at 38°C. Two thermometers will continuously monitor water bath temperatures and the readings from the thermometers and sous vide device will be recorded every two minutes. The frostbitten extremity will remain in the circulating warm water bath for 30 minutes, at which time the extremity will be evaluated to see if rewarming is complete (warm to touch, pliable tissue). Tissue that is still frozen will be placed back into the water bath for an additional 30 minutes, at which time they will be reassessed. Medical providers directly involved in the care of the patient will fill out a survey regarding viability of this method and ease of use.
Primary Objective	To assess the ability of sous vide rewarming in maintaining constant water bath temperatures and efficacy in rewarming the acutely frostbitten extremity.
Secondary Objective(s)	To determine the ease of use of sous vide water bath rewarming in the acutely frostbitten extremity.
Research Intervention(s)/ Invest. Agent(s)	ANOVA Precision® Cooker sous vide device
IND/IDE #	NA
Study Population	Patients presenting to the emergency department with acute frostbite requiring rewarming; Providers to conduct rewarming, and complete a survey
Sample Size	1-5 patients locally, with anticipation of multicenter collaboration at 5-10 additional locations with similar enrollment goals.
Study Duration for individual participants	1-2 hours
Study Specific Abbreviations/ Definitions	SVD – sous vide device, SVR – sous vide rewarming

PROTOCOL TITLE: Assessment of Sous Vide Water Baths for Acute Rewarming of Frostbitten Extremities.

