9.0 Study Timelines*

- *Describe:*
 - Each participant will be enrolled during the study period for this treatment, which includes the emergency department visit. The actual estimated treatment duration is 30 minutes. Some participants may exceed this and be treated for 60-90 minutes.
 - Given the incidence of frostbite and census of the Dartmouth-Hitchcock emergency department, and the requirement for the participant to have acute frostbite (currently frozen) rather than already thawed, it is expected to take the entire cold frostbite season to enroll 1-5 participants per study enrollment location.
 - The estimated date for the investigators to complete this study: Sept 11, 2023.

PROTOCOL TITLE: Assessment of Sous Vide Water Baths for Acute Rewarming of Frostbitten Extremities.

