24.0 Resources Available

- This research study has the support of the emergency department chair. As PI, [name] will dedicate as much time as necessary to oversee and ensure appropriate conduct of this study.
- We are working with our Director of Research Operations to ensure compliance with institutional practice and appropriate regulatory management.
- The Dartmouth-Hitchcock Emergency Department is an academic, level I Trauma center with an annual patient volume of approximately 35,000. The patient volume of other participating centers range from TBD to TBD.
- The human research component is comprised of 30-90 minutes of treatment by placing hands and/or feet in a warm water bath. As such, there is unlikely to be untoward medical or psychological consequences. Should medical or psychological consequences occur, the study is being completed in a Level I Trauma center emergency department that contains the resources to address any unforeseen issues.
- All persons assisting with the research will undergo one-on-one training with the PI regarding the recruitment plan, consent process, and research procedures including monitoring, managing, and recording data on the participant and water bath, as well as protocols for cleaning and storing the SVD. A comprehensive email containing this information will be sent to all persons assisting as a reference.

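### The Section 6 temperature log ends at 30 minutes although treatment may last 90, and the Section 15 low-temperature stops are neither listed in Section 6 nor given a counting rule

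*Combined protocol and SAP*

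**What the plan says.** All references are to the combined protocol and SAP.

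**Treatment time.** Section 6 fills the basin with "water from jugs at room temperature"; the device is then "set to maintain the bath at a constant 38°C for 30 minutes duration". Tissue is examined at 30 minutes: "If the extremity still feels cold or frozen, an additional 30 minutes in the water bath will commence". Section 1 has the same extension. Section 9 adds: "Some participants may exceed this and be treated for 60-90 minutes". Section 24 describes the research as "comprised of 30-90 minutes of treatment by placing hands and/or feet in a warm water bath".

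**Temperature log.** Sections 1 and 6 (bedside steps) call for readings every 2 minutes and name no end. The Data Collection part of Section 6 ends them once the 30 minutes of treatment are over. Section 17 describes a form with 2-minute readings over the rewarming period.

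**Stops.** The risk-reduction list in Section 6 has two: two consecutive recordings at or above 42°C, and discomfort beyond that expected. Section 15 adds a switch to manual rewarming if the bath "does not reach the target temperature in 30 minutes, or if the water bath temperature drops below 37°C for more than 5 minutes".

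**Outcomes.** Section 17 names two primary outcomes: whether the tissue rewarmed, and whether the device held the target temperature. The analysis is descriptive.

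**The concern.** The limbs that need an extension are those that thaw slowly, and for them the bath's performance is of most interest. If the log ends at 30 minutes, the extension adds nothing to the temperature outcome. The principal investigator's review after each subject (Section 18) relies on temperature recordings and would have none for that time. The 42°C stop is defined by consecutive recordings, so it would have nothing written to act on.

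The second part concerns the low-temperature stops. Staff who work from the Section 6 list see a high-temperature stop and a discomfort stop, but no action for a bath that is too cool. If a limb is switched to manual rewarming and then thaws, the outcome of whether the tissue rewarmed could be recorded as met, although the device did not do it.

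**Working it through.** The plan has no sample size calculation, power or significance level, so there is no stated figure to reproduce. The check compares sections and adds simple arithmetic.

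**1. Where the log ends**

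| Place | Interval | End |
|---|---|---|
| Section 1 | 2 min | not stated |
| Section 6, bedside steps | 2 min | not stated |
| Section 6, Data Collection | 2 min | 30 minutes |
| Section 17, collection form | 2 min | end of the rewarming period |

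One of the four sets a 30-minute end, and it conflicts with Section 17 whenever treatment is extended.

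**2. Share without readings if the 30-minute end is followed.** For total treatment time T, the share is (T − 30)/T.
- T = 30: 0/30 = 0%.
- T = 60 (one extension): 30/60 = 50%.
- T = 90 (upper figure in Sections 9 and 24): 60/90 = 67%.

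Readings per instrument, counting time zero, are T/2 + 1: 16 for 30 minutes, 31 for 60 and 46 for 90. An extended treatment therefore lacks 15 or 30 readings per instrument. With three instruments (two thermometers and the device), that is 45 or 90 per basin.

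**3. Where the low-temperature stops appear.** Both are in Section 15. Neither is in the Section 6 list of procedures that reduce risk. That list does say that standard rewarming follows an early stop, so it gives the action but not this trigger.

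**4. The clock.** The water starts at room temperature, and no section says whether the 30 minutes run from switch-on or from reaching 38°C. If from switch-on, the failure-to-heat stop falls due at the same moment as the 30-minute tissue check, and the reader must combine two sections to know what happens next. If from reaching 38°C, the two are separate.

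**5. How a switched limb is counted.** Under Section 14, withdrawal ends data collection, and data already held are analysed with a note of the early end. If a switch is a withdrawal, a later manual thaw is not collected. If it is not, no rule applies.

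The weight of one case, assuming one limb per case:
- Section 2, 5 to 20 cases: 1/20 = 5 points; 1/5 = 20 points.
- Section 1, 1 to 5 local patients plus 5 to 10 further sites with similar goals: 1 + 5 × 1 = 6 to 5 + 10 × 5 = 55 patients; 1/6 = 17 points; 1/55 = 2 points.

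The documents give no rate of device failure, so these are weights for one case and not expected errors.

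**The case against.** The safeguard exists. Section 15 gives trigger, action and continuous monitoring, and it binds wherever the rule is printed. The thermometers run throughout, so staff can see a wrong temperature even when nobody writes it down. A researcher talks the staff through the steps, and Section 24 promises one-on-one training on "research procedures including monitoring, managing, and recording data on the participant and water bath". Section 15 calls failure to heat unlikely. The 30-minute end of the log may only describe the standard treatment, and Section 14 speaks of readings within the same treatment phase, which suggests that later phases are read too. The collection forms are said to be attached but cannot be seen here; they may carry enough rows and a stop field. In a series this small, a switched case would be visible individually.

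Most of this stands, and it makes the point minor. It does not remove the conflict between the Data Collection text and Section 17, nor does it supply a counting rule.

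A reader might infer more: that the extension contradicts Section 15 and keeps a frozen limb in a cool bath past the required stop. The documents do not support that. Section 14 uses the term water bath for one maintained by hand after the device is off, and Section 15 describes the fallback as adding warm water to the basin. An extension can therefore comply with Section 15, and an overrun arises only if staff ignore that section. Nor is the absence of these stops from Sections 4 and 14 a fault: one defines endpoints, the other lists withdrawal criteria, and a change of heating method need not be a withdrawal.

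**Conclusion.** The point holds as a minor inconsistency with three parts.

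- **Log.** Followed as written, the Data Collection text leaves 50% of a 60-minute treatment, or 67% of a 90-minute one, without recorded temperatures. This is an upper bound: if Section 17 governs, the gap is zero.
- **Stops.** The two Section 15 triggers are in force but missing from the Section 6 list, where staff would look for them, and the start of the 30 minutes is undefined.
- **Counting.** Unless a switch is treated as withdrawal, a limb thawed by hand could be counted as rewarmed. One such case is worth 5 to 20 points at 5 to 20 cases, or about 2 points at 55 patients, assuming one limb per case.

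No hypothesis test is affected. The documents do not show that limbs would be left in a cool bath, and nothing here shows that patients would be harmed.

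**What to change.** 1. In the Data Collection part of Section 6, run the 2-minute log until rewarming is complete or SVR stops, so that it agrees with Section 17. Check that the attached form has enough rows.
2. Add both Section 15 stops to the Section 6 risk-reduction list. State that after a stop any extension takes place in a manually maintained bath, and whether the 30 minutes run from switch-on or from reaching 38°C.
3. Add a form field for the time and reason SVR stopped. In Section 17, report a limb switched to manual rewarming as not rewarmed by SVR.

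Sections 4 and 14 need no change.

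**Cost.** If the log now ends at 30 minutes, one extension adds 30/2 = 15 rows per basin, or 15 × 3 = 45 readings. With four basins at once that is 60 rows and 180 readings, taken by the person already logging. The SVR success proportion may come out slightly lower. No extra patients or staff are needed.
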